### **4.1.1 Obtaining Written Informed Consent**

Potential patients expressing a willingness to participate in the study will be interviewed by the Site PI or their qualified designee, and the study objectives, benefits and risks of participation, and study requirements will be thoroughly reviewed with the patient. The patient will be given a copy of the consent form to review, and adequate time will be provided to ask questions, discuss with family members, and decide about study participation. If the patient wishes to participate in the study, he/she will be required to provide written informed consent prior to any study-specific procedures commence. A copy of the signed consent form will be given to the patient and the original will be kept in the patient file with the source documents.

Note: Consenting may be conducted several weeks prior to other study procedures depending on the need for a prohibited medication washout or whether the consenting process occurred on a day other than the Monday or Tuesday after the long dialysis weekend.

### **4.1.2 Assignment of Unique Patient Enrollment Number**

Consenting patients will be assigned a unique Patient Enrollment Number comprised by a 2-digit site number, and a sequentially assigned 3-digit number starting with 001. For example, at site 01, the first enrolled patient will be assigned 01-001, the second patient 01-002, etc. If the second patient does not meet all the inclusion/exclusion criteria (e.g., the patient fails to meet the required  $K^+$  ranges), his/her Patient Enrollment Number will not be replaced, and the 3rd consenting patient will be assigned 01-003.

Upon randomization, the patients will be assigned a sequential subject number of 01 through 88.

### **4.1.3 Recording of Demographic Data**

Demographic data (date of birth, sex, self-reported race, and ethnicity) will be recorded at screening.

### **4.1.4 Review of Medical/Surgical, Laboratory, and Medication History**

Patient medical records and prior dialysis flow sheets will be reviewed to determine whether the patient meets all inclusion and none of the exclusion criteria. The review will include, but will not be limited to the following:

- 1) Routine "standard of care" laboratory data for the 2 months prior to giving written informed consent.

- 2) Routine "standard of care" determinations of the ratio of urea clearance (K) multiplied by dialysis time (t) to the volume of water in the body (Kt/V) for the 2 months prior to giving written informed consent.
- 3) Routine dialysis parameters, such as blood flow (Qb), dialysate flow (Qd), amount of fluid ultra-filtrated during dialysis (Delta UF) and post-dialysis exit weight for each of the 2 months prior to giving written informed consent.
- 4) Evidence of past history of intermittent atrial fibrillation (patients with > 3 months of continuous atrial fibrillation will be considered ineligible for study participation).
- 5) History of repeated muscle cramping (patients with such history will be identified and approached for study participation).
- 6) Past echocardiograms, if available, completed within 6 months prior to giving written informed consent. If there is echocardiographic data available, the following will be recorded for assessing and adjudicating atrial fibrillation events and any clinically significant cardiac arrhythmias, as available:
  - a) Left ventricular ejection fraction (LVEF)
  - b) Presence of distinct wall motion defects
  - c) Estimated left end-diastolic pressure
  - d) Distinct valvular abnormalities
  - e) E/A (ratio of peak velocity blood flow from left ventricular relaxation in early diastole [E wave] to peak velocity flow in late diastole caused by atrial contraction [A wave]) and E/e' (ratio of transmitral early peak velocity [E] to early diastolic mitral annulus velocity [e'])
  - f) Atrial cross-sectional diameter
  - g) Right ventricular systolic pressure.
- 7) Negative pregnancy test for females of childbearing potential to confirm eligibility.

#### **4.1.5 Physical Exam**

A complete physical examination will be performed prior to the placement of the LINQ implantable recorder, with focus on general appearance, respiratory and cardiovascular systems, and lower extremities, and will include a limited neurological exam.

#### **4.1.6 Vital Sign Measurements and Weight**

Measurement of vitals is standard of care throughout each dialysis session, and will include blood pressure, pulse, weight, and body temperature.

Measurement of vitals and weight will be recorded post dialysis on Friday or Saturday prior to the long dialysis weekend and pre-dialysis on Monday or Tuesday after the long dialysis weekend.

#### **4.1.7 12-Lead Electrocardiogram (ECG)**

A standard 12-lead ECG recording will be performed and used for confirmation of eligibility.

#### **4.1.8 K+ and PO4 Piccolo POCT System Measurements (Weeks -4 and -3)**

Patients will have blood draws completed prior to dialysis on two (2) separate occasions following the long dialytic “weekends” (i.e., on two consecutive Mondays for patients on a Monday-Wednesday-Friday dialysis schedule or on two consecutive Tuesdays for patients on a Tuesday-Thursday-Saturday dialysis schedule) during screening, before insertion of the cardiac loop recorder. Initial measurements of K+ levels will occur real-time, using the Piccolo POCT system.

Patients with two (2) separate pre-dialysis Piccolo POCT measurements of K+ between 5.1 and 6.5 mEq/L will be considered eligible for study participation and be allowed to proceed to placement of the implantable loop recorder. If one of the two screening pre-dialysis K+ levels is between 4.6 to 5.0 mEq/L or 6.6 to 7.0 mEq/L, the patient can undergo an additional whole blood Piccolo POCT K+ measurement. Patients who fail the third whole blood Piccolo POCT K+ measurement will be considered ineligible for study participation. Screen failures can be re-screened once to confirm eligibility in the study.

[figure not shown]
Note: K+ and PO4 Piccolo POCT may be performed several weeks after consenting depending on the need for a prohibited medication washout or whether the consenting process occurred on a day other than the Monday or Tuesday after the long dialysis weekend.

In addition, PO4 will be measured by the Piccolo Xpress chemistry analyzer to determine incidence of hypophosphatemia (<3.0 mEq/L).

#### **Piccolo POCT System**

The Piccolo Xpress chemistry analyzer provides quantitative in-vitro determinations of clinical chemistry analytes in lithium-heparinized whole blood, heparinized plasma, or serum. The system consists of a portable analyzer and single-use disposable reagent discs. The analyzer (see figure below) contains the following features and components (see **Figure 7** below):

- A variable-speed motor to spin the reagent disc
- A photometer to measure analyte concentrations
- two microprocessors to control testing and analytical functions
- A thermal line printer to print out results
- A WVGA color touchscreen for communicating with the analyzer
- Optional data functions for more detailed analysis information

**Figure 7 - Piccolo Xpress Chemistry Analyzer**

Each reagent disc is self-contained clear plastic, 8 cm in diameter and 2 cm thick, and containing an aqueous diluent in its center and dry reagent beads in cuvettes around its edge. All blood separation and sample diluent mixing is performed within the disc itself.

To perform an analysis, the operator needs only to collect a blood sample (lithium-heparinized whole blood or plasma, ), place the sample in the reagent disc, put the disc into the analyzer drawer on the front of the analyzer, and input patient information. When analysis is finished, the results print automatically.

Results are printed for inclusion within the patient's medical record. One Ethernet port and five USB ports are provided so data can be sent to an external printer, computer, memory stick, or laboratory information systems/electronic medical record systems (LIS/EMR).

The entire analysis requires ~100  $\mu$ L of sample and is capable of providing results in about 12 minutes.

Please refer to the Piccolo Xpress Chemistry System Operator's Manual (provided separately from this protocol) for additional details on proper use and operation of the System. All System operators should familiarize themselves with the applicable sections in the operator's manual prior to conducting testing to assure safe and effective use of the Piccolo POCT System.

[figure not shown]
#### **4.1.9 Insertion of the Cardiac Loop Recorder (Week -2)**

Patients who have completed the screening assessments and are willing to proceed with study participation will be referred to a cardiac electrophysiologist (EP) or qualified implanter who is

trained and experienced in the placement of the LINQ device. It is anticipated that arranging for placement of the device (including scheduling and actual implantation) will take approximately 1-2 weeks, but may take up to 30 days. Please contact the sponsor if ILR placement will take longer than 30 days after the last qualifying Piccolo POCT K+ System Measurements. The sponsor will determine on a case-by-case basis if an additional Piccolo POCT K+ System Measurement is required prior to Baseline.

**LINO Device Insertion**

As described in Section 8, patients with two (2) separate pre-dialysis Piccolo POCT measurements of K+ between 5.1 and 6.5 mEq/L will proceed to scheduling and placement of a LINQ cardiac loop recorder. The research staff will schedule placement of the LINQ device with a participating EP cardiologist or qualified implanter on an “off-dialysis” day. As shown in Figure 8, the Medtronic Reveal LINQ™ implantable Loop recorder is a 1.7-inch-long rectangle shaped device that is placed subcutaneously (SQ) along the left parasternal border by a trained EP cardiologist or qualified implanter. This procedure requires only local anesthesia and is approximately 20 minutes in duration. Clinicians should follow the implant manuals when performing the Reveal LINQ implant.

**Figure 8 - LINQ Insertable Cardiac Monitor**

After the LINQ device is implanted, it should be programmed to the study required settings specified below. The patient ID should be entered and it should be the CareLink Clinic code, followed by the device serial number.

It is recommended to choose “Cryptogenic Stroke” as the “Reason for Monitoring”.

Programming Parameter	Required Setting
AT/AF Detection	On
Type	AF Only
AF Detection	Balanced Sensitivity
Ectopy Rejection	Aggressive
AT/AF Recording Threshold	All Episodes
Episode Priority	Tachy, Pause, Brady

[figure not shown]
Tachy Detection	On
Tachy Interval	130 bpm
Tachy Duration	16 beat
Brady Detection	On
Brady Interval	40 bpm
Brady Duration	4 beats
Pause Detection	On
Pause Duration	3 sec

\*Recommended to be programmed to nominal settings that are automatically programmed with “Cryptogenic Stroke” as “Reason for Monitoring” with adjustments to Tachy and Brady Intervals.

### **Post-LINQ Device Insertion**

For 2 weeks after LINQ device insertion, patients will be given time to heal and adapt to the device. During this 2-week blanking period, the device will measure continuous cardiac data, but it will not be interrogated and will not be used for analysis. During this blanking period, Medtronic will train study staff on how to interrogate and transmit LINQ device data, which will be sent to the Medtronic Monitoring Service; refer to the data flow shown in Figure 9.

After the 2-week ILR post-insertion recovery period, patients will be randomized to one of two treatment sequences, as described in [Section 3.5](#). The day of randomization will be denoted as Study Day 1 and will also mark the start of Treatment Phase 1.

**Figure 9 - Cardiac Monitoring Data Flow**

1. Medtronic cardiac device is interrogated once a week in the dialysis clinic using the Patient Connector and the CareLink Express mobile app on a tablet.
2. The app will confirm that the transmission was successful.

3. Transmission will be read and triaged by the Medtronic Monitoring Service and sent to study Cardiologist for initial review.

## 4.2 Treatment period

Assessments during the treatment period will be carried out according to the schedule provided in [Table 1](#).

After completing the 2-week post-ILR insertion blanking period, patients will be switched to the dialysate arm that they had been allocated to through randomization. After a 2-week “accommodation” period to the new dialysate (Weeks 1 and 2), the cardiac monitoring blanking period will be complete, and patient’s ILRs will be interrogated weekly in order to download and transmit cardiac monitoring data. Patients will also undergo weekly Piccolo POCT blood draws initiated on Mondays or Tuesdays after their long dialysis weekends.

### 4.2.1 Blood Draws (Weeks 3 to 10 and Weeks 13 to 20)

During both 8-week treatment phases, the first twenty-five (25) patients randomized receiving standard treatment (hemodialysis using 2.0K+/2.5 Ca++ dialysate bath, without Lokelma supplementation) will undergo blood collection for select chemistry tests and determination of protein-bound uremic toxins (PBUTs).

Blood will be drawn as follows:

- 1) A 4.0 ml Green Top tube will be drawn from the dialysis line after placement of the dialysis needles and BEFORE the initiation of dialysis. The Green Top tube will be in & out inverted 3 times and then used for Piccolo POCT measurements of K+, Ca++ and PO4, as described in [Section 8](#). This will be repeated promptly before the anticipated termination of the dialysis session and within 30 minutes prior to rinse back.
- 2) Treatment Phase-1 only: Two 4.0 ml Purple Top tubes will be drawn from the first twenty-five (25) patients receiving standard treatment (hemodialysis using 2.0K+/2.5 Ca++ dialysate bath, without Lokelma supplementation) by the same method (as described above) and centrifuged. Each tube of plasma (approximately 1ml after processing) will be transferred to a 1.0 ml O-Ring sealed cryovials (two cryovials pre-dialysis and two cryovials promptly before the anticipated termination of the dialysis session and within 30 minutes prior to rinse back) and frozen at -80°C until analyzed for measurement of pre- and post-dialysis concentrations of the following PBUTs: p-Cresol sulfate (PCS), indoxyl sulfate, and asymmetric dimethylarginine (ADMA). Measurement of pre- and post-dialysis levels will be conducted by an outside vendor using gas chromatography-mass spectrometry (GC-MS) ([Tsikas et al. 2003](#)).
- 3) 5) A 5.0 ml Yellow Top SST tube will be drawn from the dialysis line promptly before the anticipated termination of the dialysis session (and within 30 minutes prior to rinse back) will be sent to the local laboratory for routine measurement of Mg++ levels.
- 4) A 2nd 4.0 ml Green Top tube will be drawn from the dialysis line promptly before the anticipated termination of the dialysis session (and within 30 minutes prior to rinse back) for Piccolo POCT measurement of post-dialysis electrolytes (K+, Ca++ and PO4), as described in [Section 8](#).

- 5) A 5.0 ml Yellow Top SST tube will be drawn from the dialysis line promptly before the anticipated termination of the dialysis session (and within 30 minutes prior to rinse back) and will be sent to the local laboratory for routine measurement of Mg++ levels upon symptomatic muscle cramping (if possible).

#### **4.2.2 Insertable Cardiac Loop Recordings (Weeks 3 to 10 and Weeks 13 to 20)**

ILR interrogation will be initiated at the end of each 2-week accommodation period (to the new dialysate) and will continue throughout the two 8-week treatment phases. Devices will not be interrogated during either 2-week accommodation periods (following randomization and cross-over) and the data recorded during that time will not be used for analysis.

Patients will undergo LINQ device interrogation on a weekly basis, on each Monday or Tuesday after their long “dialysis weekend” throughout the two 8-week treatment phases. Each download session will occur prior to the pre-dialysis vital signs and weight measurements using the Patient Connector and the CareLink Express mobile app on a tablet. This process is anticipated to take less than 5 minutes. Data will not be reviewed at the time of interrogation.

#### **Cardiac Data Monitoring**

ILR will be interrogated weekly following the long “dialysis weekend” using the Patient Connector and the CareLink Express mobile app on a tablet. Cardiac data will be managed via the CareLink network and reviewed by the Medtronic Monitoring Service, where clinically relevant cardiac data will be identified and prioritized based on clinically actionable events. If a patient’s arrhythmia meets any of the three CSCA categories, the principal study cardiologist and the site PI will be contacted to determine whether the patient requires further evaluation. Participating sites will receive copies of relevant cardiac events to enter into their patient’s medical records.

Patients participating in the study may also receive a Patient Assistant, a hand-held, battery-operated telemetry device that enables the patient to activate the recording of cardiac information in the LINQ device while experiencing or immediately after a symptomatic event (see Figure 10). During the monitoring period, patients will be instructed to mark their symptom when they sense a tachyarrhythmia, bradycardia, or irregular heart rate. These events will be reviewed during the weekly LINQ device data download in order to determine if the symptoms were associated with a cardiac event.

**Figure 10 – Patient Assistant**

### **4.2.3 Cross-Over (Week 11)**

At the end of the first treatment phase (Weeks 3 to 10) of the study, all blood draws will be stopped for 2 weeks. Cardiac loop recording devices will not be interrogated during this 2-week accommodation period, and the data recorded during that time will not be used for analysis. Patients who completed treatment with experimental 3.0 K+/2.5 Ca++ dialysate with Lokelma supplementation (on off-dialysis days) during Treatment Phase-1 will be crossed over to standard 2.0 K+/2.5 Ca++ dialysate with no Lokelma supplementation for Treatment Phase-2. Patients who completed treatment with standard 2.0 K+/2.5 Ca++ dialysate with no Lokelma supplementation during Treatment Phase-1 will cross-over to experimental 3.0 K+/2.5 Ca++ dialysate with Lokelma supplementation (on off-dialysis days) for Treatment Phase-2.

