**Table 1 Study Plan and Schedule of Assessments**

Study Period / Visit	Screening	ILR Insertion by EP cardiologist	Baseline/ Randomization	New Dialysate Accommodation Period 1	Treatment Phase 1	Cross-over	New Dialysate Accommodation Period 2	Treatment Phase 2	ILR Removal by EP cardiologist	End of Study	Reference to Protocol Section
Study Week (Wk) [* , ** or ***]	-4 to -3**	-2*	1**	1 & 2**	3 to 10**	11**	11 & 12**	13 to 20**	21-22*	22-23***	
Study Day (D)	-28 to -15	-14	1	1 to 14	15 to 70	71	71 to 84	85 to 140	Between D141 and D155	Within 1 to 14 days after ILR Removal	
Inclusion/exclusion criteria	X		X								3.1, 3.2
Day of the Week			M/T	M/T	M/T	M/T	M/T	M/T			
ILR insertion [7]		X									4.1.9
Randomization to one of two treatment sequences [6]			X								3.5
Study drug dispensed/ returned on 3.0 K+/2.5 Ca++ dialysate group				X	X		X	X			7.2.2
Cardiac Data Loop Recordings					X			X			4.2.2
K+, Ca++ and PO 4 Piccolo POCT promptly before dialysis end) [2]				X	X		X	X			4.2.1

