**Table 1 Study Plan and Schedule of Assessments**

Study Period / Visit	Screening	ILR Insertion by EP cardiologist	Baseline/ Randomization	New Dialysate Accommodation Period 1	Treatment Phase 1	Cross-over	New Dialysate Accommodation Period 2	Treatment Phase 2	ILR Removal by EP cardiologist	End of Study	Reference to Protocol Section
Study Week (Wk) [* , ** or ***]	-4 to -3**	-2*	1**	1 & 2**	3 to 10**	11**	11 & 12**	13 to 20**	21-22*	22-23***	
Study Day (D)	-28 to -15	-14	1	1 to 14	15 to 70	71	71 to 84	85 to 140	Between D141 and D155	Within 1 to 14 days after ILR Removal	
Pregnancy Test for Females of Childbearing Potential	X										

Abbreviations: AE=adverse event; Ca=calcium; ECG=electrocardiogram; EP=electrophysiologist; ILR=insertable loop recorder; K=potassium; Mg++=magnesium; PBUTs=protein-bound uremic toxins [including p-Cresol sulfate [PCS], indoxyl sulfate, and asymmetric dimethylarginine [ADMA)]; SAE=serious adverse event

\*Performed on any day. (Note: ILR placement needs to be one week prior to baseline, which starts on Mondays or Tuesdays after each long dialysis weekend.)

\*\*Performed weekly, on Mondays or Tuesdays after each long dialysis weekend. (Note: Screening ICF can be obtained on any dialysis day, but all other procedures need to be performed on Monday or Tuesdays after the long dialysis weekend. Additionally, consenting may be conducted several weeks prior to other study procedures depending on the need for a prohibited medication washout or whether the consenting process occurred on a day other than the Monday or Tuesday after the long dialysis weekend.)

\*\*\*Performed on any dialysis day

[1] K+ Piccolo POCT (utilizing full renal panel) are performed pre-dialysis, on a Monday or Tuesday after the long dialysis weekend, twice during the Screening period, and weekly during the treatment period (both 2-week accommodation periods and 8-week Treatment phases). Note: K+ Piccolo POCT may be performed several weeks after consenting depending on the need for a prohibited medication washout or whether the consenting process occurred on a day other than the Monday or Tuesday after the long dialysis weekend.

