[2] During the treatment period (both 2-week accommodation periods and 8-week Treatment phases), a second Piccolo POCT is performed promptly before dialysis end and within 30 minutes prior to rinse back on Mondays or Tuesdays after each long dialysis weekend (i.e., weekly), to measure K+, Ca++ and PO4.

[3] Applies only to the first twenty-five (25) patients randomized receiving standard treatment (hemodialysis using 2.0K+/2.5 Ca++ dialysate bath, without Lokelma supplementation) during Treatment Phase-1. Performed weekly, on Mondays or Tuesdays after each long dialysis weekend, promptly before dialysis end and within 30 minutes prior to rinse back.

[4] Performed weekly, on Mondays or Tuesdays after each long dialysis weekend, promptly before dialysis end and within 30 minutes prior to rinse back. Mg++ levels will be determined by the local laboratory at each site.

[5] Performed (if possible) upon symptomatic muscle cramping, promptly before dialysis end and within 30 minutes prior to rinse back. Mg++ levels will be determined by the local laboratory at each site.

[6] Baseline/Randomization is conducted on Week 1 of the new Dialysate Accommodation Period 1. Crossover occurs on the same day as Week 11 of the new Dialysate Accommodate Period 2. Neither Baseline/Randomization nor Crossover will be considered a separate visit.

[7] If ILR insertion is performed more than 30 days after the last K+ Piccolo POCT determination, please contact the sponsor who will determine if an additional K+ Piccolo POCT determination will be required prior to the baseline visit. These will be handled on a case-by-case basis.

[8] Adverse events will be collected from the time of first dose of Lokelmaâ, throughout the treatment and post-treatment follow-up period, up to the last study visit.

[9] SAEs will be reported from the time the patient signed the Informed Consent Form.

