### 5.1.3 Potassium Measurements

A further secondary objective of the study (see [Section 2.2](#)) is to determine whether the addition of oral sodium zirconium cyclosilicate (Lokelma®) during the 2-month treatment phase with the 3.0 K+/2.5 Ca++ dialysate bath will reduce the number of days outside the “K+ safety range” of 4.0 to 5.5 mEq/L compared to the 2-month treatment phase with the 2.0 K+/2.5 Ca++ dialysate bath.

K+ Piccolo POCT will be performed weekly during the two 8-week Treatment phases, as follows: pre-dialysis, and promptly before dialysis termination and 30 minutes prior to rinse back (along with Ca++ and PO4 measurements); see [Section 4.2.1](#).

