## 7.2 Dose and Treatment Regimens

### 7.2.1 Dosing Regimen

Patients will take Lokelma supplementation on off-dialysis days (4 days/week) while receiving hemodialysis with 3.0 K+/2.5 Ca++ mEq dialysate bath (8-week treatment phase):

- Patients on a Monday-Wednesday-Friday dialysis schedule will take the study drug on Tuesday, Thursday, Saturday, and Sunday
- Patients on a Tuesday-Thursday-Saturday dialysis schedule will take the study drug on Monday, Wednesday, Friday, and Sunday.

The individual starting dose will be 5.0 grams (4 days/week), and will be titrated weekly in 5.0 gram increments up to a maximum of 15.0 grams (4 days/week) to maintain K+ within the desired target range (between 4.0 and 5.5 mEq/L):

- Patients who fail to achieve a pre-dialysis K+ of  $\leq 5.5$  mEq/L after one week of 5.0 grams Lokelma will be treated with 10.0 grams on off-dialysis days for an additional 7 days.
- Patients failing to achieve a pre-dialysis K+ of  $\leq 5.5$  mEq/L after one week of 10.0 grams Lokelma will have their study drug dose increased to 15.0 grams.
- Patients failing to achieve the target K+ after a 7-day course of 15.0 grams Lokelma on off-dialysis days will be considered a treatment failure and withdrawn from the study.

Potassium levels will be regularly monitored throughout the 8-week treatment phase, and the study drug dose adjusted based on the potassium levels (i.e., increased [up to a maximum of 15.0 grams/day] if potassium is  $>5.5$  mEq/L, or decreased if potassium is  $<4.0$  mEq/L).

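### Section 4.2.3 stops all blood draws in Weeks 11 and 12, but Table 1 requires weekly potassium tests in those weeks, just as Sequence A starts the 3.0 K+ bath and Lokelma

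*Protocol*

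**What the plan says.** Section 4.2.3 (Cross-Over, Week 11) states that at the end of Weeks 3 to 10 "all blood draws will be stopped for 2 weeks". It calls the same window the two-week accommodation period and says that loop recorders are not interrogated in it.

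Table 1 says the opposite about blood tests. Under Accommodation Period 2 (Weeks 11 and 12, Days 71 to 84) it marks pre-dialysis Piccolo potassium, end-of-dialysis Piccolo potassium, calcium and phosphate, and local-laboratory magnesium. Footnote [1] schedules the pre-dialysis test "weekly during the treatment period (both 2-week accommodation periods and 8-week Treatment phases". Footnote [2] repeats this for the other Piccolo test: "During the treatment period (both 2-week accommodation periods and 8-week Treatment phases), a second Piccolo POCT is performed promptly before dialysis end".

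The same column of Table 1 also marks the row "Study drug dispensed/ returned on 3.0 K+/2.5 Ca++ dialysate group". Section 7.2.1 says that the dose "will be titrated weekly in 5.0 gram increments up to a maximum of 15.0 grams", with each step decided on the pre-dialysis potassium after one week at the current dose.

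Other sections point in different directions:

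- Section 4.2 begins by deferring to Table 1: "Assessments during the treatment period will be carried out according to the schedule provided in". It then introduces the weekly draws as following the accommodation period of Weeks 1 and 2.
- The Section 4.2.1 heading reads "Blood Draws (Weeks 3 to 10 and Weeks 13 to 20".
- Section 5.1.3 says that "Piccolo POCT will be performed weekly during the two 8-week Treatment phases" and does not mention the accommodation periods.

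**The concern.** Two operative parts of the current protocol give opposite instructions for the same two weeks. Section 4.2.3 is the specific instruction for the cross-over and covers all draws without exception. Section 4.3, by contrast, stops only draws outside standard of care. A site reading the cross-over section would reasonably stop testing.

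The timing is poor. At Week 11 Sequence A patients leave the 2.0 K+ bath for the 3.0 K+ bath and begin Lokelma at 5 g. They qualified for the study with post-weekend potassium between 5.1 and 6.5 mEq/L, so some may already be above the 5.5 mEq/L target. Section 1.1.1 itself names hyperkalemia between sessions as the legitimate worry about a higher-potassium bath. Several protections depend on the post-weekend pre-dialysis value:

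- the dose steps in Section 7.2.1;
- the hyperkalemia definition in Section 5.3.1;
- the limit on staying on treatment in Section 3.9, which looks at two consecutive weeks above 6.5 mEq/L.

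Without the tests in Weeks 11 and 12, none of these can operate from protocol data just after the switch. The protocol provides no data monitoring committee and no study committees (synopsis; Section 6.10).

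**Working it through.** The protocol gives no figure of its own to reproduce. The check compares the two instructions and counts days.

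**Inputs**

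- Weekly visits fall on the Monday or Tuesday after the long weekend. Week 1 starts on Day 1, cross-over is Day 71, Accommodation Period 2 is Days 71 to 84, and Treatment Phase 2 starts on Day 85 (Table 1).
- Cross-over falls on the Week 11 visit (Table 1, footnote [6]).
- The starting dose is 5 g, with steps to 10 g and then 15 g, each after one week at the lower dose with pre-dialysis potassium still above 5.5 mEq/L (Section 7.2.1).
- 44 patients are randomized per sequence, with 10% expected not to complete both periods (Section 8.2).

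**Visit days.** Day for week w = 7 × (w − 1) + 1. This gives Week 10 = Day 64, Week 11 = Day 71, Week 12 = Day 78, Week 13 = Day 85 and Week 14 = Day 92.

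**Consequences for a Sequence A patient starting 5 g at the Day 71 switch**

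| | Table 1 followed | Section 4.2.3 followed |
|---|---|---|
| Pre-dialysis potassium values | Days 64, 71, 78, 85 | Days 64, 85 |
| Longest interval between values | 7 days (71 − 64) | 21 days (85 − 64) |
| First pre-dialysis value reflecting the new bath | Day 78 | Day 85 |
| Time from switch to that value | 7 days (78 − 71) | 14 days (85 − 71) |
| Earliest step to 10 g | Day 78 | Day 85 |
| Earliest step to 15 g | Day 85 | Day 92 |
| Earliest two consecutive weekly values on the new bath | Days 78 and 85 | Days 85 and 92 |

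The Day 71 pre-dialysis value is drawn before the first session on the new bath, so it still reflects the old one. One titration decision, on Day 78, is lost.

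**Patients exposed.** 44 × 0.9 = 39.6, about 40 in Sequence A. If every Sequence A patient reaches cross-over, the number is 44.

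**Tests lost per crossing patient, either sequence.** Piccolo: 2 weeks × 2 tests = 4. Weekly magnesium (Table 1, footnote [4]) adds 2 weeks × 1 = 2. The total is 6 scheduled tests.

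**Weeks 1 and 2.** No sentence prohibits draws in the first accommodation period. The Section 4.2.1 heading, Section 5.1.3 and the second part of Section 4.2 nevertheless describe sampling as if it began at Week 3, whereas Table 1 starts it in Week 1. Sequence B patients start the 3.0 K+ bath and Lokelma in those weeks, so the same ambiguity affects them, in a weaker form.

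**The case against.** The strongest reply is that Table 1 is the governing schedule. Section 4.2 sends sites to it, it marks the tests and the drug dispensing in Accommodation Period 2, and two footnotes repeat the point. A site that dispenses and titrates weekly would probably keep testing. This stands in part: harm depends on a site following Section 4.2.3. It does not remove the contradiction, because the instruction written specifically for the cross-over is explicit and covers every draw.

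Second, Section 7.2.1 labels its dosing text as applying to the 8-week treatment phase, so titration on Day 78 could be called an inference. The label is there. However, the synopsis and Section 1.4 have Lokelma titrated for as long as the higher-potassium bath is used, the synopsis describes the blanking period as time to adjust to both the bath and Lokelma, and Table 1 dispenses drug in it. The weight of the text puts titrated Lokelma in these weeks.

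Third, the 21-day interval starts from a value on the old bath. That is fair. For the new bath alone, the comparison is 14 days against 7, a delay of one week.

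Fourth, Section 5.1.3 and the Section 4.2.1 heading do not forbid other draws; they are narrower descriptions. That is also fair. Only Section 4.2.3 prohibits anything, and only for Weeks 11 and 12.

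Finally, patients attend dialysis three times a week, and routine clinical laboratory work may supply a potassium value. The protocol schedules no such value for titration in this window.

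**Conclusion.** The contradiction is real and should be corrected. Following Section 4.2.3 leaves about 40 to 44 Sequence A patients with no protocol potassium value between Day 64 and Day 85. The first pre-dialysis check on the new bath, and each possible dose increase, then come one week later than Table 1 allows. Each crossing patient in either sequence loses four Piccolo tests and two magnesium tests.

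This rests on three assumptions: that sites act on Section 4.2.3, that Lokelma starts at 5 g on the switch and is titrated during accommodation, and that no outside laboratory value is used in place of the protocol test. The sequence labels follow Section 3.5. Table 4 reverses them, but under either labelling one sequence starts the 3.0 K+ bath at Week 11.

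The issue is patient safety and dosing. Section 4.2.2 excludes loop-recorder data from the accommodation periods, so no bias in the atrial fibrillation comparison is claimed.

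**What to change.** In Section 4.2.3, replace the general stop with one limited to loop-recorder interrogation and sampling for protein-bound uremic toxins. State that the weekly pre-dialysis and end-of-dialysis Piccolo tests and the weekly magnesium test continue in Weeks 11 and 12 as in Table 1.

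Align Section 4.2, the Section 4.2.1 heading and Section 5.1.3 so that both accommodation periods, Weeks 1 and 2 and Weeks 11 and 12, follow Table 1.

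The cost is one sentence in Section 4.2.3 and matching wording in three other places, in one protocol amendment with a memo to sites. No test is added beyond those already in Table 1.
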